3.6 Clinical measures

At each visit and at delivery, clinical data will be collected and recorded in forms designed for the study.

3.6.1 Blood pressure

Blood pressure measurements will be standardized. The equipment must be serviced locally before the initiation of the study. The subject should be at rest, seated, for 5 minutes; the cuff should be placed on the right arm at the level of the heart before the measurements. Two blood pressure measurements of systolic and diastolic will be taken using a standard sphygmomanometer at 3-minute intervals. Leave the cuff deflated on the subject's arm and wait for 3 minutes to take the second measurement. Diastolic blood pressure will be measured at the 5th Korotkoff sound, which is the disappearance of the sounds.³³

The standard sphygmomanometer will be used because its calibration and use are well established, it is considered the gold standard against which new devices have to be tested³⁴, and allows the measurement of the true systolic, diastolic, and pulse pressures.³⁵ The alternative to the use of standard sphygmomanometer would be to rely on automated devices. However, it has been observed that many automated devices were inaccurate in measuring

blood pressure.³⁶ Furthermore, the cost of a high quality automatic sphygmomanometer could be as high as USD 1000 making it prohibitive for use in this trial. Therefore, it is felt that the use of a standard sphygmomanometer is justified within the context of a pragmatic, double-blind, large trial. At every centre, the trial coordinator will train staff on their abilities to measure blood pressure according to guidelines contained in the trial document: *A practical guide on how to measure blood pressure and test for proteinuria*. The trial coordinator will be trained before the initiation of recruitment. Retraining sessions will be carried out every three months. At monthly intervals, staff will be tested for reliability of blood pressure measurements. Test-retest procedures will be performed using a double stethoscope and results of the measurements will be recorded on appropriate forms to calculate agreement between examiners.

3.6.2 Urine analysis

Midstream urine will be collected routinely, according to guidelines contained in the trial document: *A practical guide on how to measure blood pressure and test for proteinuria*, from all women receiving ANC visits, on admission in labour or before elective caesarean section to detect the presence of protein. Measurements of urinary protein will be carried out in urine samples without any visible blood contamination. For subjects with vaginal discharge samples will be taken after carefully cleaning of the introitus. In subjects with pre-labour rupture of membranes the presence of proteinuria should be verified by sterile catheter. Dipstick for qualitative urine analysis will be used in all ANC visits and at admission in the labour ward throughout the study.

3.6.3 Anthropometry

Anthropometry (weight and height) of the mother during the first antenatal visit, and birth weight of her baby will be routinely collected. The methodology will be standardized and careful quality control of equipment instituted. Women wearing light clothes will be weighed on a calibrated scale. Height will be measured without shoes.

3.7 Assessment of nutrient intake

The major reasons for documenting nutrient intake in previous studies were to determine the amount of calcium obtained from sources other than the study tablets and the quantities of other nutrients that may affect calcium absorption or retention. The nutrient intake assessment was often made by 24 hr recalls conducted at randomisation and at 32-33 weeks gestation. In the present study the populations have been selected based on existing knowledge of their calcium intake. However a formal calcium intake assessment will be done in a random sample of pregnant nulliparous women at their first antenatal visits before 20 weeks of gestation in the study clinics to ensure that these institutions currently serve a low-calcium intake population. It has been decided a priori that the population cut-off level for median calcium intake will be 600 mg/day. Centres serving a population with a higher median calcium intake will not be eligible for the trial. Following this population assessment before the trial commences, no further individual intake evaluation of enrolled women will be undertaken. This is because of the pragmatic nature of the trial, which is aimed at testing the effectiveness of the supplement in populations with general low calcium intake. The conclusion and recommendations, if the results support the need for extra calcium, will not call for an individual screening for low calcium intake before supplementation.

4 Ethical aspects

This study is designed to determine whether an increase in calcium intake during the second half of pregnancy would benefit mothers in regions where dietary calcium intakes are substantially below recommended levels. Pre-eclampsia, pregnancy-induced hypertension and eclampsia are serious health problems for women in most developing countries. Two issues merit further discussion under ethical aspects.

4.2 Participation of women

The women will be recruited at ANC clinics. It will be emphasised that enrolment in the study is voluntary, that she can withdraw at any time from all or part of the study, and that any decision she takes in this respect will have no bearing on the medical care she and her family receive. The study will be explained verbally, according to the information sheet and consent will be recorded with a signature or thumbprint.

Enrolment will be at the discretion of the staff responsible for each mother. No treatment of any kind will be withheld from a mother because of her participation in the study and mothers who develop hypertension or pre-eclampsia will be given appropriate therapy.

Informed consent for possible enrolment will be obtained antenatally following routine practices in the participating hospitals and a staff of the trial will inform women about consent for participation. Depending on local requirements, verbal consent may be considered adequate to recruit women. The consent form has been translated into local languages as necessary. The WHO approved consent form is presented in Appendix 4. Participants will not be named in any reports arising from the trial.

5 Follow-up

The study primary endpoints will be met when:

- The woman has delivered.
- Pre-eclampsia or eclampsia is diagnosed (in this case the woman should continue receiving supplements). These women must be followed up until delivery according to the study protocol.

Long-term follow-ups may be undertaken depending on their economic feasibility in subgroups of women but are not planned at this stage.

5.1 Assessment of compliance

At each monthly antenatal care visit following enrolment, the bottle which was given to the woman at the previous visit will be collected and a new bottle for the next 4 weeks will be provided. All bottles should be returned to the subject's treatment box. Every time a bottle is returned, the number of tablets left should be counted and recorded in the Subject Treatment Record form (STR). At the end of the follow-up of each subject, the total number of tablets given and returned will be calculated and recorded in the End of the Study and Delivery form (DEL).

6 Quality control procedures

6.1 Before recruitment

1. Previous RCTs conducted by some of the selected centres on this subject have assisted in optimising the procedures of the trial.
2. The survey among participating centres on baseline calcium intake of the served pregnant population will assist in determining the baseline calcium intake estimates of the study population.
3. All centres piloted the trial procedures, including the use of data collection forms.
4. Both the protocol and the trial report will include requirements laid out in the CONSORT statement.

5. Each centre has provided the Trial Coordination Unit in HRP/RHR/WHO, Geneva with their recruitment target based on their pre-trial obstetric statistics.

6.2 During recruitment

1. Completed data collection forms will be returned to WHO in Geneva monthly; data checking and entry will be continuous. All data will be double entered, cleaned and queries checked immediately with the local investigators. Prompt return of data collection forms and speedy clarification of queries will facilitate verification of data.

2. Double-blinding will reduce biases in the monitoring of women and assessment of outcomes.

3. Randomization will take place when the woman's name and hospital number is written on the next treatment box and in the subject number list. If a box is not used for whatever reason, it will be returned to WHO unopened with only the study number on it. The used boxes and bottles will be kept in the centres until the WHO site visitor has checked them.

4. Good Clinical Practice (GCP)⁴⁰ procedures will be followed.

5. A random sample of boxes will be sent for content testing to ascertain whether the content matches coding. Similarly, a random sample of tablets will be analysed to check the calcium and placebo contents. This will be conducted by the manufacturer without the involvement of the trial unit in Geneva.

6. The storage conditions will be monitored by dataloggers which record the temperature and humidity ensuring that the trial medications are kept under optimal conditions.

7. The following procedures will be adopted to standardize outcome assessment:

a) Training sessions will be conducted according to specific methods and audiovisual material developed by professional trainers in blood pressure measurements (Shared Care Inc., California) to ensure that blood pressure measurements will be standardized through all centres. Before the initiation of the trial, specialized trainers from Shared Care will standardize and certify in blood pressure measurements all the principal investigators and the field coordinators from each centres during a training session to be held at the WHO headquarters in Geneva.

- b) Intra- and inter-observer errors will be evaluated monthly during the trial using a double stethoscope according to a standard methodology developed by Shared Care Inc.
- c) Staff will undergo regular retraining sessions for blood pressure measurement every three months using the audiovisual training material developed by Shared Care Inc.

6.3 After recruitment

Data will be analysed and reported as intention-to-treat, stratification for effect modifiers will be determined a priori and the draft analysis plan follows the dummy tables enclosed. (Appendix 2).

7 Follow-up procedures

The main requirement from collaborating centres will be that women are followed from the first ANC visit before 20 weeks until delivery. The trial medications should be discontinued only if the subject refuses to take the medication, when parenteral magnesium sulphate therapy is initiated, and in case of suspicion of urolithiasis.

8 Data management and analysis

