3.1.1 Routine antenatal and postnatal care

The study will not alter or interfere with any treatment or care given routinely to women in the antenatal care clinics or delivery institutions selected for the trial. Routine measures should include at least:

1. Attendance at ANC clinics starting before 20 weeks of pregnancy (up to 19 weeks and 6 days). The frequency and content of the visits will follow the standard practice of the clinic but at least one clinical visit will be carried out every four weeks to all enrolled women.
2. Monitoring standardized blood pressure measurement and routine urine screening for proteinuria at each antenatal care visit.
3. Assessment of birth weight and gestational age at delivery or shortly afterwards.

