3.2 Intervention: calcium supplements

The women will be randomized to receive either a calcium supplement or a placebo from the time of enrolment, until delivery or initiation of any magnesium sulphate treatment, or the suspicion of urolithiasis. Women starting antenatal care before the twentieth week will be randomized at the first visit. Most of the women will therefore be supplemented for approximately five to six months. The diagnosis of pre-eclampsia or hypertension is not a reason for discontinuation of treatment.

The choice of calcium carbonate as the supplement was made because it is the cheapest of all other calcium supplements, making it more feasible for programme implementation in the case that the trial demonstrates its effectiveness and because all published studies and an ongoing trial in the Gambia have used this salt. Furthermore, several studies have demonstrated the absorption of calcium carbonate to be higher in comparison with other calcium salts.

There will be three chewable tablets containing 500 mg elemental calcium to be taken every day. Women will be instructed to chew tablets at meals, but at least 3 hours away from any iron supplements^{30 31 32}. The control group will receive three tablets a day of identical characteristics, colour and taste as the intervention tablet prepared and packed by the same pharmaceutical manufacturer.

All women will be encouraged not to take any additional calcium supplements. For those women who need analgesics, acetaminophen, and for those needing antacids, a non-calcium antacid will be recommended.

The dose 1500 mg/day, lower than the 2000 mg/day used in previous trials was selected for the following reasons:

- a) The study populations have an intake level (median < 600 mg/day) that will be raised to a level above the RDA of 1200 mg with 1500 mg/day supplementation.

b) This level of calcium intake is more likely to be achievable from dietary sources alone. In this way, if the trial shows beneficial results from supplementation, the populations will not have to depend solely on supplementation by tablets.

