3.3.2 Exclusion criteria

Women will be excluded under the following conditions:

- History of urolithiasis or symptoms suggestive of urolithiasis or any renal disease such as haematuria, flank pain, etc.
- Parathyroid disease.
- Blood pressure ≥ 140 mmHg systolic or ≥ 90 mmHg diastolic, receiving treatment or had history of hypertension.
- Taking diuretics or any digoxin treatment.
- Plan to deliver in a health facility outside the study area or at home.
- Taking phenytoin or tetracyclines.

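### Section 7's closed list of reasons to stop the tablets has no clinician-initiated safety stop and conflicts, taken literally, with the GCP commitment in section 8.6 (minor)

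*Protocol*

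**What the plan says.** Section 7 (Follow-up procedures) sets the stopping rule: "The trial medications should be discontinued only if the subject refuses to take the medication, when parenteral magnesium sulphate therapy is initiated". The sentence ends with one further reason, suspected urolithiasis. That makes three reasons: the woman's refusal and two medical events.

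Section 3.2 (Intervention) defines how long tablets are taken: "until delivery or initiation of any magnesium sulphate treatment, or the suspicion of urolithiasis". The two medical triggers are the same as in section 7. It then names conditions that do not end treatment: "The diagnosis of pre-eclampsia or hypertension is not a reason for discontinuation of treatment". On duration it says "Most of the women will therefore be supplemented for approximately five to six months".

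Section 3.3.2 (Exclusion criteria) is wider at entry. It excludes "History of urolithiasis or symptoms suggestive of urolithiasis or any renal disease such as haematuria, flank pain, etc" and, separately, "Parathyroid disease".

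Other sections bear on safety in general terms:
- Section 3.1.1: "The study will not alter or interfere with any treatment or care given routinely to women in the antenatal care clinics".
- Section 4.2 lets the woman withdraw from some or all of the study and promises that no therapy is held back because she takes part.
- Sections 6.2 and 8.6 commit the trial to GCP; section 8.6 does so specifically for reporting and handling adverse events.
- Section 8.1 requires serious adverse events to be recorded and sent in within 24 hours.
- Section 8.3 says the intervention does not hold up standard management of a complication, and gives a route to unblinding if it is needed.

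**The concern.** A stopping rule for study medication protects participants, and this one is stated as exhaustive. Staff who follow the sentence as written may stop tablets on their own initiative for two events only: magnesium sulphate or suspected stones. For any other medical reason, stopping depends on the woman declining.

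The protocol itself gives reason to think the list too short. It treats parathyroid disease and any renal disease as grounds for not starting 1500 mg of calcium a day, yet after entry only suspected stones remain on the list. It also foresees serious adverse events but says only how to record and report them, not what to do about the tablets.

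What is at stake is clear authority for staff in eight centres in seven countries, over several months of dosing. The estimate of the treatment effect is not at stake.

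**Working it through.** The point concerns wording, so the check is whether any section supplies a route for a clinician to stop tablets.

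| Event after enrolment | On the list in section 7 or 3.2? | Bars entry under 3.3.2? | Listed ground for a clinician to stop |
|---|---|---|---|
| Magnesium sulphate started | Yes | Not applicable | Yes |
| Suspected urolithiasis | Yes | Yes | Yes |
| Haematuria or flank pain | Indirectly, where stones are suspected | Yes | Usually yes |
| Renal disease not suggesting stones | No | Yes | None |
| Parathyroid disease | No | Yes | None |
| Serious reaction thought related to the tablets | No | Not applicable | None |
| Hypertension or pre-eclampsia arising in the trial | Expressly not a reason (3.2) | Hypertension: yes | None, by design |

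Three rows have no listed ground. Do the general safeguards fill them?
- Sections 3.1.1 and 4.2 (care): they concern giving other care, not stopping trial tablets.
- Section 4.2 (withdrawal): this is the woman's decision.
- Section 8.1: recording and reporting only.
- Section 8.3: it allows the allocation to be revealed; it does not mention stopping.
- Sections 6.2 and 8.6: GCP handling of an adverse event would be expected to allow stopping. This is the closest to a remedy, and it is also where the conflict lies, because a specific 'only' points one way and a general commitment the other.

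The protocol gives no event rate, so the defect itself cannot be sized. What can be checked is whether the sample size tolerates a few more stops.

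Inputs from section 3.5.1: 8500 women, so n = 4250 per arm; placebo rate p0 = 4%; calcium rate p1 = 2.8%; stated power 80%. Assumptions: two-sided 5% test; a share s of calcium women stop and lose all benefit (pessimistic), so the calcium rate becomes p1 + s × (p0 − p1).

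With p̄ the mean of the two rates,

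power = Φ{ [p0 − p1 − 1.96 √(2p̄(1 − p̄)/n)] / √([p0(1 − p0) + p1(1 − p1)]/n) }.

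At s = 0: (0.012 − 1.96 × 0.003931) / 0.003929 = 1.093, giving power 86.3%. The stated 80% is therefore met with some room.

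| s (assumed) | Calcium rate | Power, 4250 per arm |
|---|---|---|
| 0 | 2.800% | 86.3% |
| 0.5% | 2.806% | 85.9% |
| 1% | 2.812% | 85.5% |
| 2% | 2.824% | 84.8% |
| 7.63% | 2.892% | 80.0% |

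The break-even share is 0.0763 × 4250 = 324 calcium women. For the protocol's more conservative case (3.5% against 2.45%, 4500 per arm), power goes from about 83.5% at s = 0 to 83.0% at s = 0.5% and 81.8% at s = 2%. These figures price the remedy; they do not measure the fault.

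**The case against.** The strongest reply is that only a harsh reading of one sentence produces the problem. Section 8.6 covers the handling of adverse events, not just their reporting, and puts it under GCP; a clinician working to GCP would probably stop the tablets after a serious reaction. The woman may refuse or withdraw at any time, and nothing prevents a clinician advising her to. The renal examples in section 3.3.2, haematuria and flank pain, would often raise the suspicion of stones that already triggers a stop. Calcium carbonate is described in section 4.1 as a common antacid without specific contraindications in pregnancy, and the one hazard discussed there, stones, is on the list. A Manual of Operations (section 10.1.2, not shown) may deal with single cases.

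Most of this stands, and it sets the weight. It does not remove the word 'only', and no section says that GCP handling takes precedence over it.

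Three stronger readings are tempting and are not supported:
- *Women would be kept on unsafe tablets.* The documents do not show this. GCP, withdrawal and standard care all work against it.
- *Every entry exclusion, including the excluded drugs, should be a stop.* Section 3.3.2 gives no reason for the drug exclusions, the protocol describes no interaction hazard, and section 3.2 deliberately continues tablets after hypertension or pre-eclampsia. Planned place of delivery is not a safety matter either.
- *The results are compromised.* Analysis is by intention to treat (sections 6.3 and 8.5), and section 7 has women followed to delivery.

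**Conclusion.** The point holds as a minor drafting fault in a participant-safety rule. Read literally, sections 7 and 3.2 leave no clinician-initiated stop for a serious reaction thought related to the tablets, for new parathyroid disease, or for renal disease that does not suggest stones, and the closed list conflicts with section 8.6. The number of women affected is unknown, and no effect on the results is claimed. The conclusion rests on the protocol text alone; an operations manual could soften it in practice but would still sit under a protocol sentence that says otherwise.

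**What to change.** In section 7, delete 'only' and add: *or when the responsible clinician judges that continuing is medically unsafe (for example a serious adverse event thought related to the tablets, or newly diagnosed parathyroid or renal disease); hypertension or pre-eclampsia is not by itself a reason to stop.* Mirror this in section 3.2 and record the reason for each stop. Leave follow-up to delivery, blinding and intention-to-treat analysis unchanged.

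The cost is one sentence in two places, one recorded item and perhaps a few more discontinuations. Under the assumed range in the working, power stays above 80% in both of the protocol's scenarios, so the sample size need not change.

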8.1 Data management

Data will be collected prospectively by the researchers at the local collaborating centre and forms will be sent to the UNDP/UNFPA/WHO/World Bank Special Programme of Research, Development and Research Training in Human Reproduction (HRP) of the Department of Reproductive Health and Research at WHO headquarters in Geneva monthly following the standard data management procedures of HRP/RHR.

The researchers will record side effects. Although it is very unlikely that serious adverse events will occur, these will be recorded in special forms and will be returned by the local investigators to the Trial Coordination Unit (HRP/RHR/WHO in Geneva) by facsimile within 24 hours of the event. These procedures have been used in multiple multicentre^{REFNOTA} trials and proved to be very efficient and compliant with the Good Clinical Practice (GCP) principles and data management.⁴⁰ Furthermore the investigator will report all adverse events in a timely and correct manner to the local authorities according to local national law. The WHO coordinating unit will share this information with Nycomed Pharma.

Data entry will be done centrally in Geneva.

